## **Management of Hypertension**

For patients experiencing an increase in systolic and/or diastolic blood pressure that is persistent and may be associated with the study treatment, recommendations for the clinical management of hypertension are described in Table 7.

Table 7 Management and Dose Modification Guidelines for Hypertension

Hypertension	Action and Dose Modification
Scenario A:  Asymptomatic and persistent a SBP of ≥140 and <160 mmHg, or DBP ≥90 and <100 mmHg,  or  Clinically significant increase in DBP of 20 mmHg (but still below 110 mmHg).	Continue study treatment at the current dose  Adjust current or initiate new antihypertensive medication  Titrate antihypertensive medication(s) during the next 2 weeks as indicated to achieve well-controlledb BP  If BP is not well controlled within 2 weeks, consider referral to a specialist and go to scenario (B).
Scenario B:  Asymptomatic SBP ≥160 mmHg, or DBP ≥100 mmHg,  or  Failure to achieve well-controlled BP within 2 weeks in Scenario A	Interrupt study treatment if clinically indicated  Adjust current or initiate new antihypertensive medication(s)  Titrate antihypertensive medication(s) during the next 2 weeks as indicated to achieve well-controlled BP  Once BP is well controlled b , restart study treatment reduced by one dose level
Scenario C:  Symptomatic c hypertension  or  Persistent d SBP ≥160 mmHg, or DBP ≥100 mmHg, despite antihypertensive medication and dose reduction of study treatment	Interrupt study treatment  Adjust current or initiate new antihypertensive medication(s)  Titrate antihypertensive medication during the next 2 weeks as indicated to achieve well-controlled BP  Referral to a specialist for further evaluation and follow-up is recommended  Once BP is well controlled, restart study treatment reduced by one dose level
Scenario D:  Refractory hypertension unresponsive to above interventions or hypertensive crisis.	Permanently discontinue study treatment Continue follow-up per protocol.

Abbreviations: BP = blood pressure; DBP = diastolic blood pressure; mmHg = millimetres mercury; SBP = systolic blood pressure;

- a. Hypertension detected in two separate readings during up to three consecutive visits
- b. Well-controlled blood pressure defined as SBP ≤140 mm Hg and DBP ≤90 mm Hg in two separate readings during up to three consecutive visits.
- c. Symptomatic hypertension defined as hypertension aggravated by symptoms (e.g., headache, light-headedness, vertigo, tinnitus, episodes of fainting) that resolve after the blood pressure is controlled within the normal range.
- d. Persistent hypertension is defined as asymptomatic hypertension after initially successful anti-hypertensive intervention.

#### 5.8.3.3. Guidelines for Prolonged QTc

Guidelines for dose modification and stopping criteria due to QTC-prolongation are provided in Table 8.

Table 8 Withholding and Stopping Criteria for QTc-Prolongation

QTc-Prolongation a	Action and Dose Modification	
QTcB ≥501 msec	Interrupt study treatment until QTcB prolongation resolves to grade 1 or baseline	
	Restart at current dose level b	
	If event recurs, permanently discontinue study treatment	

Abbreviations: msec = milliseconds; QTcB = QT interval on electrocardiogram corrected using the Bazett's formula

- a. Based on average QTc value of triplicate ECGs. For example, if an ECG demonstrates a prolonged QT interval, obtain two or more ECGs over a brief period, and then use the averaged QTc values of the three ECGs to determine if study treatments should be interrupted or discontinued.
- b. If the QTc prolongation resolves to grade 1 or baseline, the patient may resume study treatment if the investigator and GSK medical monitor agree that the patient will benefit from further treatment.

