# 7.4.8. Electrocardiograms (ECG)

Twelve (12)-lead ECGs will be obtained using an ECG machine that automatically calculates heart rate and measures PR, QRS, QT, RR and QTcB intervals.

At each assessment, a single 12-lead ECG will be performed by qualified site personnel after the patient has rested in a semi-recumbent or supine position for at least 5 minutes.

See Section 5.8.3.3 for instructions if QTc withholding criteria are met.

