8. GENERAL CONSIDERATIONS FOR DATA ANALYSES

8.1. Reporting Conventions

Data will be listed and summarized according to GlaxoSmithKline (GSK) current reporting standards where applicable. Integrated Data Standards Library (IDSL) standards will be followed, as appropriate. Reporting and analyses will be performed

using SAS, Version 9.2 or higher. These SAS programs will be imported into HARP and the final output will be produced by running drivers in HARP. Final delivery of all statistical displays will be generated using Clinical Data Interchange Standard Consortium (CDISC) standards. Other software may be used as needed.

Deviations from the analysis in the RAP will be identified in the Clinical Study Report (CSR).

Unless otherwise stated, all listings will be sorted by centre, subject number, and visit. Unless otherwise stated, continuous variables will be summarized with the statistics mean, median, standard deviation, minimum, and maximum. Categorical variables will be summarized with frequency counts and percentages.

Unscheduled visits will be included in the listing using actual time and in calculation of maximum or minimum value over time. However, unscheduled visits will not be included in summaries by planned time.

For summary by planned time, not all plan times are needed to be included in the summary table.

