9.2.9. Multiple Assessments

All data will be reported according to the nominal visit date for which it was reported (that is, no visit windows will be applied during dataset creation). Unscheduled data is included only in summary sections and in shift summaries of laboratory (e.g., vital signs/ECG) data labelled worst- case. For summaries that collapse data across multiple planned time intervals, select the worst-case data at each collapsed interval.

If multiple assessments on different days are reported for the same scheduled assessment, then the latest assessment for that scheduled assessment will be analyzed.

If multiple assessments are reported on the same date for the same scheduled planned time, then the worst-case result will be analyzed, with the exception of laboratory data reported from both central and local laboratories. If laboratory data is reported from both central and local laboratories with the same date, then the central laboratory data will be analyzed to provide consistency with measurements from other subjects. For example, for ECG data where 3 assessments are collected for each scheduled planned time, the first 3 measures will be used to compute the mean values for ECG intervals at each scheduled planned time.

Data from all assessments (scheduled and unscheduled), including multiple assessments, will be included in listings.

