12.8. Other Safety Measures

Vital Signs

Values of vital signs as well as the change from baseline will be summarized by scheduled visit using mean, median, standard deviation, minimum and maximum.

In addition vital signs or blood pressure values will be categorized as follows:

- Systolic Blood Pressure (BP) (mmHg): Grade 0 (<120), Grade 1 (≥ 120 -<140), Grade 2 (≥ 140 -<160) and Grade 3 (≥ 160)
- Diastolic BP (mmHg): Grade 0 (<80), Grade 1 (≥ 80 -<90), Grade 2 (≥ 90 -<100), and Grade 3 (≥ 100)
- Heart rate: <60, 60-100, and >100
- Temperature: <35, 35-38, ≥ 38

Summaries of increase in vital signs or blood pressure from the baseline with respect to the categories defined above will be performed. These summaries will display the number and percentage of subjects with any grade increase, increase to grade 2 and increase to grade 3 in the worst case post baseline only.

Performance Status

ECOG performance status will be summarized at baseline and each post baseline scheduled visit. Summaries will use frequency and percentage of subjects at each planned assessment time. A summary of change from baseline by scheduled visits will be performed, as well as the worst case post-baseline and the best case post-baseline changes during the study (improved, no change, deteriorated).

A supporting listing will also be provided.

EKG

A summary of the number and percentage of subjects who had normal and abnormal (clinically significant and not clinically significant) ECG findings will be displayed by scheduled visits as well as for the worst case post baseline.

The QTc values based on Bazett formula will be rounded to the integer and the values will be categorized into the following ranges: Grade 0 (<450), Grade 1 (450-480), Grade 2 (481-500), and Grade 3 (≥ 501). Summaries of grade increase will be provided. These summaries will display the number and percentage of subjects with any grade increase, increase to grade 2 and increase to grade 3 in the worst case post baseline only.

The changes in QTc values will be categorized into the clinical concern ranges which are specific to changes in QTc: 31-60 and > 60 msec. A summary of change in QTc value will display the number and percentage of subjects with a change within each range in the worst case post baseline only. Subjects with missing baseline values will be excluded from this summary.

The summaries for the QTc will use the calculated value based on Bazett formula.

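### SAP 9.2.9 gives two incompatible rules for repeat ECGs, so the worst-case QTc tables can show Grade 3 in a patient whose triplicate mean stayed below the protocol's 501 msec criterion

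*Protocol*

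**What the plan says.** **Protocol.** Section 7.4.8 schedules one ECG per visit: "At each assessment, a single 12-lead ECG will be performed by qualified site personnel". Footnote 12 of the Time and Events table agrees. Table 8 in Section 5.8.3.3 sets its criterion at "QTcB ≥501 msec", and footnote a qualifies it: "Based on average QTc value of triplicate ECGs". The extra ECGs are taken over a brief period after one ECG shows a prolonged QT, and the instruction is then to "use the averaged QTc values of the three ECGs to determine if study treatments should be interrupted or discontinued". For reporting, Section 9.3.5.3 (Other Safety Measures) asks for worst-case ECG summaries that cover scheduled and unscheduled visits after the first dose.

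**SAP.** Section 9.2.9 states: "If multiple assessments are reported on the same date for the same scheduled planned time, then the worst-case result will be analyzed". The only exception it names is laboratory data reported by both central and local laboratories. Offered as an example, and for a design with three ECGs at every planned time, it then says that "the first 3 measures will be used to compute the mean values for ECG intervals at each scheduled planned time". Repeats on different days for the same scheduled assessment take the latest value. Section 8.1 says: "Unscheduled visits will be included in the listing using actual time and in calculation of maximum or minimum value over time". Section 12.8 puts Grade 3 QTcB at 501 msec or more and reports "increase to grade 2 and increase to grade 3 in the worst case post baseline only". Changes of 31-60 and above 60 msec are handled in the same way. These are Tables 3.6030 and 3.6040.

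**The concern.** Scheduled ECGs are single, so same-day replicates arise mainly from the check that footnote a prescribes. The handling of replicates therefore matters most for readings near 501 msec, where the Grade 3 boundary lies.

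An average is not an example of a worst-case rule, so the two sentences in 9.2.9 cannot both govern the same three ECGs. Two programmers could each follow the SAP and produce different Grade 3 counts. On the worst-case route, repeating the ECG cannot lower the tabulated grade and can only raise it, although the protocol repeats the ECG so that no treatment decision rests on one reading. The QTc table could then show a Grade 3 patient with no matching QTc interruption in the dosing record, and the reader would have to work out why from the listings.

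**Working it through.** The plan states no figure on this point, so there is none to reproduce. The check compares the rules and then sizes the gap under stated assumptions.

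**1. One triggered triplicate under each rule.** Illustrative readings are 506, 492 and 490 msec, with the first as the scheduled ECG.

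| Reading of the SAP | Value used | Grade (12.8) |
|---|---|---|
| ECG sentence overrides, repeats filed at the planned time | (506 + 492 + 490)/3 = 496 | 2 |
| Same-date worst-case sentence applies | 506 | 3 |
| Two repeats filed as unscheduled | maximum over time = 506 | 3 |

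The Table 8 value is 496 in every row, so the criterion is not met. In the third row only one ECG sits at the planned time, so there are not three to average.

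**2. Change from baseline.** SAP 9.2.7 takes the screening ECG as baseline, which is one reading under the protocol. The footnote there about averaging replicates is attached to vital signs, physical and ophthalmic examination, not to ECG. With an illustrative baseline of 442, the worst-value route gives 506 − 442 = 64 (above 60 msec) and the mean route gives 496 − 442 = 54 (31-60 msec).

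**3. Direction.** The maximum of three readings is never below their mean. For same-day repeats the discrepancy can only add Grade 3 or above-60 cases.

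**4. Size.** The documents give no QTcB distribution. Assumed inputs: true on-treatment QTcB normal with mean μ = 440 or 450 and between-patient SD s = 20 or 25 msec; within-day SD w = 8, 12 or 15 msec. Each ECG is the true value plus independent error. Each of the 12 settings was simulated with 4 million patients.

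Share with a triplicate mean below 501, given a first ECG of 501 or more:

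| μ, s | w = 8 | w = 12 | w = 15 |
|---|---|---|---|
| 440, 20 | 53% | 69% | 76% |
| 450, 20 | 44% | 60% | 68% |
| 440, 25 | 34% | 49% | 58% |
| 450, 25 | 30% | 42% | 50% |

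In these patients the worst value exceeds the mean by about 7 to 18 msec on average.

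How often the first ECG reaches 501: P = 1 − Φ((501 − μ)/√(s² + w²)).
- Lowest (440, 20, 8): 61/√464 = 2.83, so P ≈ 0.0023.
- Highest (450, 25, 15): 51/√850 = 1.75, so P ≈ 0.040.

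Expected discordant patients per ECG assessment, with 54/3 = 18 per arm:
- Lowest: 18 × 0.0023 × 0.53 ≈ 0.02.
- Highest: 18 × 0.040 × 0.50 ≈ 0.36.

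Over all 54 patients this is about 0.07 to 1.1. Rounding each reading to whole milliseconds moves the upper ends only slightly, to 77% and 0.38 per arm. The count covers only patients whose first ECG is at least 501. A first reading that is prolonged but lower, followed by a repeat of 501 or more, would add some.

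**The case against.** A reader might infer that the SAP contradicts the protocol on how QTc is judged. The documents do not support that. Footnote a governs whether treatment is interrupted or stopped; it does not say how ECGs are tabulated. The protocol's own reporting rule in Section 9.3.5.3 already asks for a worst case over scheduled and unscheduled visits. A treatment criterion and a descriptive safety table may use different values.

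A reader might also infer that the QTc tables will be inflated. That too goes beyond the text. The ECG sentence in 9.2.9 can be read as a specific rule that overrides the general one. On that reading, repeats filed at the planned time are averaged and the discrepancy disappears. Repeats on different days take the latest value, which can lie below the mean. That unscheduled replicates enter the maximum one by one is an inference, since Section 8.1 is silent on replicates within a visit.

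The practical stakes are modest. The study is descriptive, without treatment comparison, and worst-case reporting is a recognised conservative choice for safety. All ECG values are listed (Listing 30.0241), and findings that lead to interruption or discontinuation are recorded as adverse events.

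What stands is the contradiction within 9.2.9, its three-per-visit premise that does not fit this protocol, and the lack of any rule for triggered repeats filed as unscheduled. A conservative choice is legitimate, but the SAP has to make it, and here it specifies both options.

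**Conclusion.** The point holds as an ambiguity inside the SAP with a one-sided consequence, not as a conflict between protocol and SAP. On two of the plausible readings, a single triggering ECG decides the worst-case QTc result although the triplicate mean did not meet Table 8. On the third reading there is no discrepancy.

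Few patients are likely to be involved: about 0.02 to 0.36 per arm of 18 per ECG assessment, with more over several visits. Among first readings of 501 or more, about 30% to 77% have a mean below 501. These sizes rest entirely on the assumed QTcB mean and SDs. The contradiction and the upward direction for same-day repeats do not. One reclassified patient moves an arm's Grade 3 rate by 1/18 = 5.6 percentage points, which is visible in a descriptive table. Whether the Table 8 clinical criterion is right is not judged here.

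**What to change.** In SAP 9.2.9 and 12.8:

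- Exempt ECG intervals from the same-date worst-case sentence and delete the premise of three ECGs per planned time.
- State that same-day ECG replicates, whether filed as scheduled or unscheduled, are averaged first, and that the worst case over visits is then taken for Tables 3.6030 and 3.6040. This fits protocol Section 9.3.5.3, which speaks of visits and not of replicates within a visit.
- Say how many replicates enter the mean, since footnote a allows more than three.
- Keep every individual ECG in the listings.

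The cost is a few sentences and a small programming step. The downside is that isolated high readings would appear only in the listings, and Grade 3 counts may be slightly lower. The change affects the analysis only and leaves the Table 8 criterion as it is.

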## 5.8.3.4. Guidelines for Valvular Toxicity

- Patients who have an asymptomatic, moderate regurgitation or stenosis by ECHO
  (Grade 2 mitral/tricuspid/aortic valvular toxicity per CTCAE v4.0) should
  temporarily discontinue study treatment and have a repeat evaluation by ECHO
  within 1 week. ECHO should be repeated every 1-2 weeks for 4 weeks or until valve
  recovery to baseline.
  - o If the valve recovers to baseline any time during the next 4 weeks, after consultation and approval of the GSK medical monitor, the patient may be restarted on dabrafenib at a reduced dose(s). For such patients, monitoring of the valve via ECHO will then be performed 2 and 4 weeks after rechallenge, and every 4 weeks thereafter for 12 weeks and then per protocol.
  - o If repeat ECHO does not reveal valve recovery to baseline within 4 weeks, then the patient should permanently discontinue study treatment. The valve should continue to be monitored via ECHO every 4 weeks for 16 weeks or until resolution.
- Patients with a Grade 3 or 4 (symptomatic, severe regurgitation/stenosis by imaging, with symptoms controlled by medical intervention) valvular toxicity must discontinue study treatment. Valvular toxicity should continue to be monitored every 4 weeks for 16 weeks or until resolution. If recovery occurs (return to baseline via imaging AND symptom resolution) within 4 weeks, the patient may restart dabrafenib at a reduced dose after consultation and approval of the GSK medical monitor. For such patients, monitoring of the valve via ECHO will then be performed 2 and 4 weeks after rechallenge, and every 4 weeks thereafter for 12 weeks and then per protocol.

ECHO must be performed at baseline and at follow-up visit(s). Copies of all ECHO(s) and cardiology consultations performed on patients who experience a valvular toxicity will be required by GSK for review.

#### 5.8.4. Guidelines for Skin-related Adverse Events

Cutaneous adverse events have been observed in patients receiving dabrafenib, trametinib or both therapies in combination (see the Investigator Brochures for more information). Recommendations for supportive care and guidelines for dose modifications are provided (Section 5.8.4.1, Section 5.8.4.2, and Section 5.8.4.3). The institutional standards for the management of skin-related AEs can differ from these guidelines. In this case, best clinical judgment should be applied and a consultation with the GSK Medical Monitor may be required. In addition, biopsies of any new skin lesions especially those suspicious of cuSCC for further study should be taken at the investigator's discretion.

#### 5.8.4.1. Rash

Rash is a frequent AE observed in patients receiving trametinib, dabrafenib, or the combination of both therapies. Guidelines for rash management are based on experience with other MEK inhibitors and epidermal growth factor receptor (EGFR) inhibitors and are provided below (Table 9 and Table 10).

Table 9 Guidelines for Supportive Care of Rash

Type of Care	Action	
Prevention/Prophylaxis a	Avoid unnecessary exposure to sunlight	
	
 
Apply broad-spectrum sunscreen (containing titanium dioxide or zinc oxide) with a skin protection factor (SPF) ≥15 at least twice daily.
 
	
	Use thick, alcohol-free emollient cream (e.g., glycerine and cetomacrogol cream) on dry areas of the body at least twice daily.	
Symptomatic Careb	Pruritic lesions: cool compresses and oral antihistamine therapies	
	Papulopustular rash: topical steroids and antibiotics and antibiotics	
	Fissuring lesions: , silver nitrate, or zinc oxide cream	
	Desquamation: thick emollients and mild soap	
	Paronychia: antiseptic bath, local potent corticosteroids in addition to oral antibiotics; if no improvement, consult dermatologist or surgeon	
	Infected lesions: appropriate bacterial/fungal culture-driven systemic or topical antibiotics	

Abbreviations: BID = twice daily; SPF = skin protection factor

- a. Rash prophylaxis is recommended for the first 6 weeks of study treatment
- Patients who develop rash/skin toxicities should be seen by a qualified physician and should receive evaluation for symptomatic/supportive care management

Guidelines for management and dose reduction for rash considered to be related to study treatment are provided in Table 10.

Table 10 Management and Dose Modification Guidelines for Rash

CTCAE Grade	Adverse Event Management	Action and Dose Modification
Grade 1	
 
Initiate prophylactic and symptomatic treatment measuresa
 
Use moderate strength topical steroidb
 
Reassess after 2 weeks
 
	
 
Continue study treatment
 
If rash does not recover to baseline within 2 weeks despite best supportive care, continue topical steroid, consider using more potent topical steroids
 

Grade 2	
 
Initiate prophylactic and symptomatic treatment measures
 
Use moderate strength topical steroidb
 
Use systemic tetracycline
 
Reassess after 2 weeks
 
	Continue study treatment  If no recovery to ≤grade 1 within 2 weeks, reduce study treatment by one dose level. If rash recovers to ≤grade 1 within 2 weeks, increase dose to previous dose level
Grade ≥ 3	
 
Use moderate strength topical steroidsb PLUS oral
 
Use antibiotic
 
Consult dermatologist
 
	
 
Interrupt study treatment until rash recovers to grade ≤1
 
Restartc with study treatment reduced by one dose leveld
 
If no recovery to grade ≤2 within 4 weeks, permanently discontinue study treatment
 

Abbreviations: CTCAE = Common Terminology Criteria for Adverse Events

- a. Rash prophylaxis is recommended for the first 6 weeks of study treatment
- b. Moderate-strength topical steroids: hydrocortisone 2.5% cream or fluticasone prioprionate 0.5% cream
- c. Approval of GSK medical monitor is required to restart study treatment after >4 weeks of interruption.
- Escalation of study treatment to previous dose level may be considered if no rash is evident 4 weeks after restarting study treatment

### 5.8.4.2. Guidelines for Hand-foot Skin Reactions (HFSR)

Episodes of Hand-foot Skin Reaction (HFSR) have been observed in patients receiving dabrafenib. Guidelines for management of HFSR are based on experience with other kinase inhibitors (Lacouture, 2008; McLellan, 2011) and are listed Table 11.

Table 11 Management and Dose modification Guidelines for Hand-Foot Skin Reaction (HFSR)

CTCAE Grade	Adverse Event Management	Action and Dose Modification
Grade 1ª	
 
Life style changes recommendedb
 
Initiate symptomatic treatmentc if clinically appropriate
 
	Continue study treatment at current dose level
Grade 2	Life style changes recommended b	Interrupt study treatment until recovery to ≤grade 1 d
	Initiate symptomatic treatment c	Recovery to ≤grade 1 within 7 days:     Restart study treatment at previous     dose level
		No recovery to grade ≤1 within 7 days or ≥ 2 nd occurrence: restart with study treatment reduced by one dose level e
Grade ≥3	Life style changes     recommended b	Interrupt study treatment until recovery to ≤ grade 1
	
 
Initiate symptomatic treatmentc
 
Consult dermatologist
 
	Restart with study treatment reduced by one dose level e
	2 2 1 0 2 1 1 2 1 1 2 1 2 1 2 1 2 1 2 1	If 3 rd occurrence, discontinue study treatment permanently

Abbreviations: CTCAE = Common Terminology Criteria for Adverse Events

- a. A full-body skin examination and a removal of pre-existing calluses and keratotic skin is recommended prior to initiation of study treatment
- b. Life-style changes: (1)reduce exposure of hands and feet to hot water, (2) avoid traumatic activity including vigorous exercise especially in the first 4 weeks after start of study treatment, (3) avoid constrictive footwear, (4) avoid excessive friction on the skin, when applying topical treatments, (5) wear thick cotton socks and gloves, and shoes with padded insoles
- c. Symptomatic Treatments: (1) use moisturizing creams frequently and especially on hands and feet (2) consider topical keratolytics: urea 20-40 % cream, or salicylic acid 6%, or tazarotene 0.1% cream, or fluorouracil 5% cream; (3) erythrematous areas: clobetasol propionate 0.05% ointment; (4) Pain: topical lidocaine 2%, and / or systemic pain medication such as nonsteroidal anti-inflammatory drugs, codeine, and pregabalin
- c. Symptoms usually resolve within 2-4 weeks of treatment cessation. Approval of GSK medical monitor is required to restart study treatment after ≥21 days of interruption
- d. Escalation of study treatment to the previous dose level is allowed if no HFSR is observed in the 4 weeks subsequent to dose reduction.

